### **The proliferation marker Ki67 is a promising biomarker of short-term response to tamoxifen.**

There is a strong rationale and existing data to support Ki67 as a biomarker in BC prevention studies. In women with AH, Ki67 in the atypia lesion is a time-dependent marker of long-term BC risk, with higher 10-year BC risk in women with Ki67 $\geq$ 2%.[22] We have also reported that Ki67 in background normal lobules in SA is associated with long-term BC risk,[23] similar to recent findings reported in the Nurses Health Study in BBD tissues.[24] Furthermore, Ki67 is also reduced after short courses of tamoxifen. In several prospective window-of-opportunity trials of Tam (ranging from 3-8 weeks of treatment), Ki67 levels in background normal breast lobules show relative reductions of ~50% with oral tamoxifen doses of 5, 10, or 20 mg per day.[19-21] Recently, we have developed a method to quantitate Ki67 (as % cells positive) in benign breast tissues using digital image assessment with Aperio algorithms. Within 40 samples, the digital image measure of Ki67 % cells positive in background normal lobules correlated very strongly with a manual pathologist score ( $r = 0.95$ ).

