Mean treatment duration was 47 days for TAM and 44 days for 4OHT gel ( $p=0.2$ ). The median absolute decline in Ki67 (post-treatment compared to pre-treatment) was significant in the TAM (-3.7%,  $p<0.001$ ) but not in 4OHT gel arm (-1.3%,  $p=0.2$ ); between-arm  $p=0.002$ . Ki67 results following menopausal stratification also favored the TAM arm, especially in postmenopausal women: between-arm  $p=0.06$  in 37 premenopausal women and  $p=0.02$  in 35 postmenopausal women. Breast tissue 4OHT concentrations were lower (although not significantly) in the 4OHT arm in both superficial and deep tissue samples compared to the TAM arm (mean superficial tissue concentrations were 6.1 and 4.2 ng/g for TAM and 4OHT gel, respectively,  $p= 0.55$ ; and in deep tissues were 5.7 and 3.8 ng/g, respectively,  $p= 0.06$ ). Endoxifen (another active metabolite of tamoxifen) was abundant in plasma (11 ng/mL) and deep tissue (13 ng/g) of TAM arm, but present in only trace amounts in the 4OHT gel arm (undetectable in plasma and 0.31 ng/g in tissue), between-arm  $p <0.0001$ . Circulating TAM responsive markers (insulin like growth factor 1, sex hormone binding globulin, von Willebrand factor, and protein S total) and vasomotor symptoms were significantly and unfavorably modulated by TAM, but not by 4-OHT gel therapy.

**In summary, these trial results showed that the anti-proliferative effect of 4 mg/day transdermal 4OHT gel was inferior to 20 mg oral TAM in DCIS.** Tissue 4OHT concentration in gel treated subjects was lower, especially in deep tissues, although this did not quite reach significance ( $p=0.06$ ). Endoxifen exposure was markedly higher with oral TAM therapy and is a likely explanation for the inferiority of 4-OHT gel. The study authors recommended that in future studies, use of higher 4OHT gel doses may overcome this difference.

**Safety Data on 4OHT gel dose 8 mg/day.** Safety data is available for the 8 mg/day dose from a BHR Pharma sponsored study of 4OHT gel for reduction in breast density (BHR-700-301, see attached Investigator's Brochure February 10, 2022, pages 59-60). In this trial 149 subjects with dense breasts (BI-RADS C/D) received 8 mg/day 4OHT gel and 73 subjects received placebo for up to 52 weeks.

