*Statistical analysis.* The primary hypothesis is that the reduction seen with 4-OHT gel will be *not inferior* to that seen with oral tamoxifen. We also hypothesize that oral tamoxifen and 4-OHT gel will each be superior to placebo with respect to the percent change in Ki67 in background normal lobules between baseline and four weeks. Analyses will assess if significant changes in Ki67 are observed after four weeks of treatment by paired t-tests/Wilcoxon signed rank tests, stratified by treatment group. We will assess the non-inferiority of 4-OHT gel compared to oral tamoxifen by estimating a 95% confidence interval for the mean *difference* in percent change between the two agents after four weeks of treatment; if the lower limit of the confidence interval is less than the non-inferiority margin (described below), we will conclude that 4-OHT gel is non-inferior to oral tamoxifen. As exploratory analyses, we will assess pairwise differences between samples on active treatment (oral tamoxifen or 4-OHT gel, separately and combined) vs. placebo using two-sample t-tests/Wilcoxon rank sum tests. Similarly, we will assess changes from baseline in the expression of the candidate genes identified in Aim 2 (absolute log2 fold-change > 2 and/or q-value < 0.05). Volumetric density changes from baseline within treatment group will be assessed continuously, and evaluated using paired t-tests on the log-transformed density or Wilcoxon signed-rank tests; pairwise differences between treatment groups will be assessed with two-sample t-tests/Wilcoxon rank sum tests. BPU on MBI is measured as a four category ordinal scale; we will compare pre-to-post changes within group using Wilcoxon signed rank tests and will compare the percent of subjects decreasing BPU category by one or more level between groups using chi-square tests. We will assess the correlation between changes in volumetric density and changes in BPU, using Spearman correlation. Symptoms from the BCPT survey are measured on a five-level ordinal scale. We will compare differences in pre- to post-treatment symptom severity changes across

treatment arms using Wilcoxon rank sum tests.

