**Sample size/power.** Prior studies suggest that oral tamoxifen will lead to a 50% mean relative reduction in Ki67 in normal lobules at four weeks compared to baseline.[19-21, 43] We assume that the standard deviation for the percent change in Ki67 is 30 percentage points, estimated based on a plausible range from published literature.[19-21, 43]] A sample size of 36 per active treatment arm will provide >80% power at  $\alpha=0.05$  to test the hypothesis that 4-OHT gel is not inferior to oral tamoxifen with a non-inferiority margin of 20 percentage points (e.g., if oral tamoxifen results in a 50% mean reduction of Ki67, 4-OHT gel will be considered non-inferior if we can conclude that 4-OHT gel results in a mean reduction of Ki67 of at least 30%). Further 18 subjects enrolled in a placebo arm will provide >90% power to detect a mean difference of 50% reduction for either treatment arm versus an assumed mean difference of 0% for placebo assuming a two-sided, two-sample t-test with  $\alpha=0.05$ . Therefore n=90 subjects are required, but the study will over-accrue by 15% (n=104 patients) to account for cancellation, ineligibility, non-evaluable samples, or major treatment deviations.

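### The non-inferiority rule for gel against tamoxifen is worded in the wrong direction, and the hypothesised placebo comparisons have no bearing on the conclusion

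*Combined protocol and SAP*

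**What the plan says.** All of this is in section 11.0 of the combined protocol and SAP, unless stated.

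- **Decision rule.** Non-inferiority is judged from a 95% confidence interval for the difference in percent change in Ki67 between the two active arms. It is concluded "if the lower limit of the confidence interval is less than the non-inferiority margin". The direction of subtraction is not stated. The margin is 20 percentage points. No other condition applies, and the October 2022 dose update and Table 1 add none.
- **Placebo hypothesis.** "We also hypothesize that oral tamoxifen and 4-OHT gel will each be superior to placebo".
- **Status of the placebo tests.** "As exploratory analyses, we will assess pairwise differences between samples on active treatment (oral tamoxifen or 4-OHT gel, separately and combined) vs. placebo".
- **Placebo power statement.** "Further 18 subjects enrolled in a placebo arm will provide >90% power to detect a mean difference of 50% reduction for either treatment arm". That calculation takes the placebo change to be zero and uses a two-sided t-test at 0.05.
- **Within-arm tests.** "Analyses will assess if significant changes in Ki67 are observed after four weeks of treatment by paired t-tests/Wilcoxon signed rank tests, stratified by treatment group".
- **Expected tamoxifen effect.** A 50% mean relative reduction. The Ki67 background text agrees: "Ki67 levels in background normal breast lobules show relative reductions of ~50% with oral tamoxifen".

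**The concern.** There are two linked problems.

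First, the rule looks at the wrong end of the interval. If positive values mean the gel does worse, non-inferiority needs the upper limit below +20. If negative values mean the gel does worse, it needs the lower limit above -20. Requiring the lower limit to be less than the margin matches neither.

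Second, even a correct gel-tamoxifen interval cannot tell two working drugs from two that do nothing. This trial randomises placebo patients who could settle that. The plan hypothesises the result and states power for it, but does not say what a failed placebo comparison does to the non-inferiority claim. At stake is whether a positive result shows that the gel lowers Ki67 at all.

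**Working it through.** **Inputs (section 11.0).** 36 tamoxifen, 36 gel and 18 placebo patients; SD of percent change 30; margin 20; two-sided 95% interval; planned tamoxifen effect 50 points against 0 for placebo. Let T be tamoxifen's true effect over placebo and D the gel's true shortfall against tamoxifen. For an inactive gel, D = T.

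**1. Reproduce the plan's power.** SE = 30 × √(2/36) = 7.07. With D = 0 and the conventional rule, power = Φ(20/7.07 − 1.96) = Φ(0.87) = 80.7% (79.7% with the t distribution). This matches the stated 80%. For placebo, SE = 30 × √(1/36 + 1/18) = 8.66, and power at 50 points is 99.99%, consistent with the stated >90%.

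**2. The rule as written**, applied to gel-minus-tamoxifen percent change (negative = reduction). P(pass) = Φ((20 − D)/7.07 + 1.96).
- D = 20: Φ(1.96) = 97.5%, where a valid rule gives 2.5%.
- D = 30: Φ(−1.41 + 1.96) = 70.7% (71% with the SD estimated).
- D = 50: 1.3% (SD estimated).
- D = 0: Φ(2.83 + 1.96), essentially 100%. The stated 80% power therefore cannot come from this wording.

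**3. The corrected rule.** P(pass) = Φ((20 − D)/7.07 − 1.96). At D = 20 this is Φ(−1.96) = 2.5% whatever the SD, so 20 points is the boundary.

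**4. Adding the condition that tamoxifen beats placebo** (two-sided 0.05). Simulation of 36/36/18 with SD estimated, 2,000,000 trials per row. Inactive gel:

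| T (points) | As written | Corrected | Corrected, tamoxifen must beat placebo |
|---|---|---|---|
| 50 | 1.3% | 0% | 0% |
| 30 | 71% | 0.04% | 0.02% |
| 20 | 97.5% | 2.5% | 0.7% |
| 15 | 99.6% | 10.3% | 1.7% |
| 10 | >99.9% | 28.6% | 2.5% |
| 0 | 100% | 79.7% | 1.2% |

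**5. What the condition costs** when both drugs are equally active (power without it is about 79.7% throughout):

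| T (points) | Tamoxifen must beat placebo | Gel must beat placebo instead |
|---|---|---|
| 50 | 79.7% | 79.7% |
| 30 | 73% | 76% |
| 20 | 46% | 54% |
| 15 | 27% | 36% |
| 10 | 13% | 19% |

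At T = 50, the tamoxifen condition takes power from 55% to 54% if the SD is 40, and from 39% to 34% if it is 50.

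**6. What passing the condition shows.** Significance needs an observed tamoxifen-placebo difference of about 2.007 × 8.66 = 17.4 points. It establishes an effect above 0, not above the 20-point margin.

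**The case against.** The strongest reply is that the placebo problem lies outside the plan's own assumptions. Prior data in the documents point to a tamoxifen effect near 50 points, where an inactive gel essentially never passes a correct rule. The discouraging evidence concerns the gel: the background reports that "the anti-proliferative effect of 4 mg/day transdermal 4OHT gel was inferior to 20 mg oral TAM in DCIS". In that study oral tamoxifen, at 20 mg/day, did lower Ki67 significantly. The placebo and paired tests will be run anyway, so a trial in which nothing worked would be visible. Below 20 points the condition also blocks true non-inferiority most of the time (power 27% at 15 points, 13% at 10). Choosing between a tamoxifen and a gel condition is a judgement. All of this stands, and it limits the second part to a safeguard. The paired tests are not a full substitute, because they are not tied to the conclusion and cannot separate a drug effect from a change common to all arms.

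On the rule's wording, the sample-size example (a 30% gel reduction against 50% for tamoxifen) and the 80% power show that the conventional rule was intended. That makes a slip likely, but the sentence is still the stated decision rule.

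Three stronger readings are tempting:
- **That the placebo arm was sized for the superiority test.** The documents only attach a power statement to 18 patients. Five placebo patients against 36 would already give 92.6% at 50 points, so nothing shows that 18 was derived from this test.
- **That the missing placebo condition inflates type I error.** It does not. Below 20 points even an inactive gel is truly within the margin; the difficulty is what non-inferiority then means.
- **That tissue sampling will shift Ki67 in every arm.** Baseline tissue may be a diagnostic biopsy from up to 6 months before enrollment, and post-treatment tissue may be surgical (section 5.0, footnotes 8 and 9). A common shift is therefore possible, but the documents give no size for it, and footnote 8 restricts hormone use and requires at least 4 normal TDLUs.

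**Conclusion.** The concern holds in two parts of unequal weight. The interval rule is an error in a stated decision rule: under the assumptions of 36 per arm and SD 30, it passes a gel that falls 20 points short of tamoxifen in 97.5% of trials, and one that falls 30 points short in 71%. The absence of a placebo condition matters only after that correction, and then only if tamoxifen's effect over placebo is below 20 points. Nothing in the documents supports so small an effect, although the 50 points rests on change from baseline and an assumed 0% for placebo. That part should be fixed because it is cheap at the planned effect, not because failure is likely.

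**What to change.** Before unblinding, amend the statistical analysis text of section 11.0 as a fixed sequence with no split of alpha:

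1. Define the difference as gel minus tamoxifen percent change in Ki67, negative meaning reduction. Non-inferiority requires the upper 95% limit to be below +20. Equivalently, for a difference in reductions, the lower limit must be above -20.
2. Make tamoxifen against placebo (two-sided 0.05) a condition for any non-inferiority claim. If it fails, report the gel-tamoxifen interval descriptively.
3. If non-inferiority is shown, test gel against placebo (two-sided 0.05) as a key secondary. If that fails, state that non-inferiority does not establish gel activity.
4. In every case, report the tamoxifen-placebo 95% interval beside the 20-point margin.

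The cost is SAP wording only, since the placebo patients are already in the design. No power is lost at 50 points; the losses at smaller effects are in the second table above and should be accepted knowingly. A condition on gel against placebo alone is an acceptable and less costly alternative. It holds an inactive gel to about 2.4%, but does not show that the comparator worked. The correction in step 1 is needed whichever is chosen: with the present wording, an inactive gel would still pass in 60% of trials at T = 20 and about 65% at T = 30, even with the tamoxifen condition in place.

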## Background Parenchymal Uptake (BPU) on MBI is a promising noninvasive imaging biomarker of response.

Molecular breast imaging (MBI) is a low-radiation dose nuclear medicine test that uses a high-resolution, semiconductor-based gamma camera to image the uptake of Tc-99m sestamibi in the breast.[33] As MBI is a functional imaging technique that relies on differences in preferential uptake of Tc-99m sestamibi in metabolically-active cells, it is able to reveal cancers hidden among dense fibroglandular tissue on a mammogram (published incremental cancer detection of 7.5-16.5 per1000 women screened).[34, 35] In addition to detecting BC, MBI also depicts the level of Tc-99m sestamibi uptake in non-cancerous background fibroglandular tissue, termed background parenchymal uptake (BPU). BPU is subjectively assessed according to a validated lexicon as one of four categories (photopenic, minimal to mild, moderate, and marked), with high reader agreement (inter-reader  $\kappa=0.84$ , intra-reader  $\kappa=0.87$ ) that describe the relative intensity of uptake in fibroglandular tissue.[36, 37] Importantly, BPU was recently shown to be associated with BC risk; women with moderate or marked BPU have 3.4 to 4.8-fold increased risk compared to women with photopenic or minimal-mild BPU, even when adjusted for percent mammographic density and hormonal influences. The exact mechanism of uptake of Tc-99m sestamibi in breast tissue is not entirely understood, but has been correlated with blood flow, mitochondrial activity, and mitotic activity in BCs.[38, 39] In a recent study led by [name], women with high BPU on screening MBI underwent 4 weeks of low-dose (5 mg or 10 mg) oral tamoxifen, with early decreases in BPU (**Fig 1**).[40] Therefore BPU is promising as a non-invasive measure of proliferative activity in the breast tissue.

[figure not shown]

Figure 1. Images from a patient with mammographically dense breasts undergoing supplemental screening with MBI (A,B) and MBI again after 4 weeks low-dose (5 mg) oral tamoxifen (C).

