#### 5.0 Test Schedule

Test & Procedures	Baseline	End of Treatment (at the end of 4 weeks of treatment) 
Pregnancy Test (serum or urine)	X 	
Follicle stimulating hormone (FSH)	X 	
Baseline labs [CBC and Liver Function testing (ALP, ALT, AST, ALB, TP, BILI), creatinine coagulation labs (fibrinogen, Antithrombin 3)]	X 	X 
Physical Examination	X 	X 
Two 10 ml amounts of blood (will be stored for future research)	X 	X 
Blood Draw (4-OHT bioavailability)		X 
Research Biopsy of Breast Tissue - same quadrant as diagnostic biopsy  [Ki67, NanoString, 4-OHT bioavailability (post-treatment only);] Pretreatment diagnostic biopsy is OPTIONAL if meets requirements	X 	X 
Digital Screening Mammogram	X 	X 
MBI (Mayo Clinic site only)	X 	X 
BCPT Symptom Survey	X 	X 
Symptom /safety/AE assessment	X 	X 

1. For women of childbearing potential only.
2. Research Funded (Note: clinical surgical consult will not be research funded.)
3. For women with unknown menopausal status
4. Physical exam could be done within 3 months before treatment starts.

5. Blood for storage two 10 ml blood draws using purple top EDTA tubes – protect from light exposure (i.e., wrap in tin foil, use light sensitive brown bags). **First EDTA tube**- Aliquot (1) 4000uL blood pour for DNA extraction. Refrigerate, Centrifuge at lab standards. Process for three 1 ml aliquots of plasma into 3 cryovials 1 ml plasma each and 1ml WBC. Light Sensitive. Store in -80 freezer. **Second EDTA vial** is stored as whole blood.
6. Blood for 4-OHT bioavailability. 4 ml. green top heparin tube. Process for plasma. Protect from light exposure as light sensitive (i.e., wrap in tin foil, use light sensitive brown bags). Store in -80 freezer.
7. Baseline Pretreatment research tissue core biopsy information is located in Appendix F.

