## **11.0 Statistical Considerations**

The primary hypothesis is that the reduction in Ki67 will not be inferior to that seen with oral tamoxifen. A sample size of 36 per treatment arm (36 receiving oral tamoxifen and 36 receiving 4OHT gel, with 18 placebo controls) will provide >80% power at  $\alpha=0.05$  to test this hypothesis. Volume density and MBI will be compared across study arms from pre-to post-treatment. Risk predictors identified from Nanostring-based mRNA expression assay (conducted under IRB 75-87) and biomarkers of tamoxifen response (conducted under IRB 15-000279) will also be tested.

*Randomization and intervention.* To achieve the planned sample size of N=90 women, we will over-accrue by ~15% to allow for cancellation, ineligibility, non-evaluable samples, or major treatment deviations and thus plan to enroll a total of N=104 at two study sites (42 at Mayo-Rochester, 42 at Northwestern University, 20 at MD Anderson Cancer Center at Cooper). Patients will be randomized 2:2:1 to oral Tam (10 mg/day), 4-OHT gel (4 mg/each breast/day), or placebo controls for four weeks. Estimated numbers of randomized subjects to each arm will be: 42 to oral Tam, 42 to 4OHT gel, and 21 double placebo, in order to arrive at final sample size of 36, 36, and 18. Treatment randomization will be stratified with respect to menopausal status (pre- vs. postmenopausal), diagnosis (ADH vs ALH/LCIS vs increased BC risk based on risk model calculations), and study site. Oral and gel placebos will be used to create a double-blinded study. After four weeks, blood draw, physical exam, BCPT symptom survey, digital mammogram (and MBI in Mayo subjects) will be repeated. A second breast tissue sample will be obtained from the same quadrant, either as a core biopsy or as tissue adjacent to the surgical excision site.

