*Feasibility.* At Mayo Clinic in Rochester, MN, we see an average of 55 patients per year with ADH or ALH who would be eligible for this study. At Mayo Clinic, Drs. [name], [name], and [name] have successfully led accrual of over 500 women to prospective studies in the last six years, therefore successful accrual of women to this prospective study is feasible. At Northwestern University, there is a similar volume of women with diagnoses of ADH or ALH, and they have accrued ~400 women over five years to various studies requiring some form of intervention (either medication or biopsy). Accrual plan is for 42 subjects at Mayo Clinic, 42 at Northwestern University and 20 subjects at MD Anderson Cancer Center at Cooper. With an anticipated timeframe of 48 months to complete accrual, this averages to 1-2 patients per month per site. This study should be acceptable to patients as the duration of intervention is short and therefore short-term

toxicity is expected to be limited to only temporary vasomotor symptoms.

*Translational studies.* The primary endpoint will be change in Ki67 in background normal breast lobules (% cells positive by Aperio quantitation). Additional endpoints will include changes in volumetric density (% and dense volume) measured using VolparaTM both at baseline and after four weeks of treatment. In addition, promising genes from discovery work in Aim 2 will be evaluated using NanoString.

Changes in background parenchymal uptake (BPU) on MBI will also be employed as an exploratory endpoint. Blood samples and residual breast tissues collected pre/post Tam will be stored for future correlative studies.

*Endpoints.* The primary endpoint is change in Ki67 level pre/post treatment. The primary analysis for the primary endpoint will include all eligible patients who began study drug intervention and have available tissue measures of Ki67 levels at both timepoints (pre- and post-treatment).

A sensitivity analysis for the primary endpoint will also be performed. This sensitivity analysis will include eligible patients who have available tissue measures of Ki67 levels at both timepoints and were compliant with study treatment. Patients will be classified as non-compliant with the study treatment (and thus excluded from the sensitivity analysis) using criteria outlined above (patients who have less than 80% compliance with daily drug use or have missed more than 3 doses in the final 14 days).

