As for the primary endpoint, primary analyses for secondary endpoints will include all eligible patients who began study drug and have available endpoint measurements at both timepoints; sensitivity analyses for each secondary endpoint will exclude non-compliant patients (as defined above). For analyses of adverse events, all patients who started the study treatment will be included, regardless of treatment compliance or availability of endpoint measurements at both timepoints.

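### The between-arm BPU responder test counts women who are photopenic at baseline and cannot fall a category, so any such women shrink the arm difference and cost power; how many there are is not known

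*Combined protocol and SAP*

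**What the plan says.** **Scale.** Section 2.0 (BPU on MBI) describes uptake as read into "one of four categories (photopenic, minimal to mild, moderate, and marked"), in order of relative intensity. Section 11.0 repeats that "BPU on MBI is measured as a four category ordinal scale".

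**Tests.** Section 11.0 (Statistical analysis) has a within-arm Wilcoxon signed rank test of pre-to-post change. Between arms, it "will compare the percent of subjects decreasing BPU category by one or more level between groups using chi-square tests".

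**Analysis set.** Under Endpoints in Section 11.0, primary analyses of secondary endpoints "include all eligible patients who began study drug and have available endpoint measurements at both timepoints". Nothing is said about baseline category.

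**Selection.** Neither eligibility (Section 4.0) nor the stratification factors (Section 6.0) use BPU. The study cited in Section 2.0 to motivate the endpoint was different: there, "women with high BPU on screening MBI underwent 4 weeks of low-dose (5 mg or 10 mg) oral tamoxifen".

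**Numbers.** Section 5.0 limits MBI to the Mayo site. "Accrual plan is for 42 subjects at Mayo Clinic, 42 at Northwestern University and 20 subjects at MD Anderson Cancer Center at Cooper", and "Patients will be randomized 2:2:1 to oral Tam (10 mg/day), 4-OHT gel (4 mg/each breast/day), or placebo controls for four weeks".

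**Status.** Section 3.0 lists BPU change among the secondary aims. The Translational studies paragraph of Section 11.0 calls it exploratory.

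**The concern.** A response is a fall of at least one category, and no category lies below photopenic. A woman who starts there stays in the denominator of her arm but can never enter the numerator, whatever she is given. The motivating study chose women with high uptake, who had room to fall. This trial takes over the endpoint without that selection.

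Randomisation should spread such women evenly, so the comparison stays unbiased under the null. Even spread does not protect power, because the same fixed block of non-responders pulls every arm's percentage towards zero and the arms towards each other. What is at stake is the chance of seeing a real BPU effect in a small single-site sample. The reported percentages would also depend on how many photopenic women happened to enrol.

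**Working it through.** **Plan's own figure.** The documents give no power, response rate or sample size for BPU, so there is nothing to reproduce for this endpoint.

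**Inputs from the documents.** 42 Mayo women, allocation 2:2:1, 15% attrition (Section 11.0).

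- Randomised at Mayo: 42 × 2/5 = 16.8, 16.8 and 42 × 1/5 = 8.4, so about 17/17/8.
- Evaluable: 42 × 0.85 = 35.7, split 14.3/14.3/7.1, so about 14/14/7.

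**Assumed inputs (not in the documents).**

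- f, the share photopenic at baseline: 10, 20 or 30%.
- Response among women able to fall: 60% (also 50% and 40%) on active drug, 10% on placebo.

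**Step 1: the contrast.** With all women kept, a response rate p becomes (1 − f)p, so the arm difference is multiplied by (1 − f). For 60% v 10%:

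- f = 10%: 54% v 9%, 45 points instead of 50.
- f = 20%: 48% v 8%, 40 points.
- f = 30%: 42% v 7%, 35 points.

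**Step 2: does the larger n compensate?** Let D be the arm difference and p̄ the pooled response among women able to fall. Apart from a common factor, the large-sample chi-square noncentrality is:

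- all women: n(1 − f)²D² / [(1 − f)p̄(1 − (1 − f)p̄)] = n(1 − f)D² / [p̄(1 − (1 − f)p̄)]
- restricted: n(1 − f)D² / [p̄(1 − p̄)]

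The ratio of all women to restricted is (1 − p̄)/(1 − (1 − f)p̄), which is below 1 whenever f > 0. At f = 10% and p̄ = 0.3 it is 0.70/0.73 = 0.96. At f = 30% and p̄ = 0.4 it is 0.60/0.72 = 0.83. So the extra women do not make up for the smaller contrast.

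**Step 3: exact power.** All 2×2 tables were enumerated for the uncorrected chi-square test (two-sided 5%), one active arm against placebo. Keeping all women uses rates (1 − f)p on the full n. Restricting uses rates p, averaged over the binomial number of women able to fall. Entries are all women v restricted.

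| Sample | Response | f = 10% | f = 20% | f = 30% |
|---|---|---|---|---|
| 14 v 7 | 60% v 10% | 56 v 61% | 47 v 55% | 37 v 46% |
| 14 v 7 | 50% v 10% | 39 v 42% | 31 v 36% | 23 v 29% |
| 17 v 8 | 60% v 10% | 61 v 68% | 50 v 62% | 39 v 55% |
| 17 v 8 | 50% v 10% | 41 v 48% | 32 v 42% | 23 v 36% |

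With a weaker effect and few floor women (14 v 7, 40% v 10%, f = 5%), power is 24% either way.

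**Step 4: type I error (14 v 7, f = 10 to 30%).** With a common response rate of 10% among women able to fall, rejection is 3.3 to 4.2% with all women and 2.4 to 3.0% restricted. At 30% it is 6.1 to 6.2% v 4.7 to 5.1%. At 50% it is 5.0 to 5.7% v 5.5 to 5.7%. The small departures from 5% reflect the discreteness of the test in samples this small. Neither choice of denominator inflates error systematically.

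**Step 5: how much is the floor and how much is n?** At 17 v 8 with no photopenic women at all, power is 70% for 60% v 10% and 49% for 50% v 10%. At f = 30% and 60% v 10%, restricting gives 55% and keeping everyone 39%. Of the fall from 70% to 39%, restriction recovers 16 points. The other 15 are lost because fewer women can respond.

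**The case against.** The strongest reply is that the deciding input is missing. A reader might infer that photopenic women are sure to enrol in number. The documents do not say so. Section 2.0 ties moderate or marked BPU to higher breast cancer risk and Section 4.0 selects women at raised risk, so the share could be small or nil. This stands: the loss is conditional on f.

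A reader might also take the 17 v 8 gain (39 v 55% at f = 30%) as the expected benefit. That ignores the plan's own 15% attrition. At 14 v 7 the gain is 9 points, from 37 to 46%.

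Nor does restriction always win. Under Fisher's test at 17 v 8 and f = 10% it loses slightly (32 v 29% for 50% v 10%; 54 v 52% for 60% v 10%). Fisher's test is not the planned one, and under the planned chi-square no active-v-placebo scenario examined lost power. But placebo cells are already sparse, and restriction makes them sparser.

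Two further points are fair. The all-women percentage is a valid randomised comparison that follows the stated analysis set, so restricting changes the target population rather than correcting a bias. And the within-arm signed rank test, in its standard form, drops zero changes, so women who stay photopenic do not dilute it.

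What survives is narrow: for the planned between-arm test, women who cannot respond add no information about the effect and cost power if there are any.

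**Conclusion.** The point holds as a conditional and minor one. For any f > 0 the responder contrast shrinks by the factor (1 − f). With 60% v 10% response and 14 v 7 evaluable women, keeping everyone costs about 5, 7 to 8 and 9 points of power at f = 10, 20 and 30%. The cost is larger without attrition, and about nil at f = 5% with a 40% v 10% effect. The response rates and f are assumptions.

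The documents do not support reading this as a biased comparison or a type I error problem. Nor does it show that the floor is the reason the BPU comparison is weak: 17 v 8 is underpowered even with nobody photopenic. The primary Ki67 analysis is not affected.

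**What to change.** Before unblinding, amend the BPU sentence in Section 11.0 so that:

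- the between-arm responder comparison is made among women above photopenic at baseline;
- the number photopenic at baseline is reported for each arm;
- the all-women comparison is kept as supportive.

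The subset is defined by a scan taken before treatment starts, in a double-blind trial, so the randomised comparison is preserved. The baseline MBI is already scheduled, so no new data are needed. It would also help to state once whether BPU is secondary or exploratory.

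The cost is a smaller denominator. At f = 30%, 14 v 7 becomes about 14 × 0.7 = 9.8 v 7 × 0.7 = 4.9, with sparser placebo cells, and the result applies only to women able to fall. The change does not make the comparison adequately powered.
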